#### **Statistical Analysis**

*Our first aim is to demonstrate that preterm infants receiving a standardized, parent-supported, auditory-tactile intervention in addition to standard of care in the NICU will have more typical cortical multisensory processing at discharge to home and better sensory adaptation and motor and language outcomes than infants receiving only standard of care.*

For Aim 1, the between-group differences will be tested on ERP-measured multisensory processing after completion of intervention, sensory reactivity and adaption at Year 1, and motor and language ability at Year 2.

## Protocol Title: Trial to Improve Multisensory Neural Processing, Language & Motor Outcomes in Preterm Infants

---

When the dependent variable is continuous, we will use ANOVAs when controlling for pretreatment variables and independent sample t-tests when there is no need for a covariate. When testing the nominal form of the sensory reactivity and adaptation outcome, we will use logistic regression.

*Statistical power:* Using PASS software, the estimated power using a 1-tailed test for an effect size based on the pilot data (Hedges  $g = .74$ ) with a sample size of 180 is over 99%. Even if the actual effect size is  $g = .35$ , we will have over 80% power to detect the effect under the proposed conditions. Detecting the required minimum effect size is probably for a number of reasons.

First, the expected effect size for the proposed treatment on multisensory processing should be larger than that derived from the pilot because the treatment used in the pilot

(i.e., skin-to-skin contact *without* the suck-contingent presentation of parent's voice) and theory strongly suggests the multisensory treatment will produce a larger effect than a unisensory treatment. Secondly, a medium main effect size of the proposed treatment on neurodevelopmental outcomes is expected because multisensory processing is moderately to strongly associated with later neurodevelopmental outcomes.

*Our second aim is to test the role of multisensory responses at discharge in mediating intervention effects on later sensory adaptation, and motor and language outcomes.*

Mediation models are presented in Figure 3. The indirect effect (the product of the a path coefficient \* the b path coefficient) will be tested for significance using the bias-corrected bootstrap method. The a path is the main effect of treatment on the ERP measure of multisensory processing. The b path is the association of the ERP measure of multisensory processing with the outcome controlling for the treatment group.

[figure not shown]
*Statistical power:* Using simulation data, an indirect effect produced by paths each with at least the mid-point between small and medium effect sizes (0.26; i.e., at least 6.8% of the variance of the criterion variable accounted for in each path) will be detected with over 80% power when using a sample size of 180. For example, if paths a and b each have an effect size of 0.26, a significant indirect effect will be detected with 80% power with 148 participants, far fewer than the proposed sample size of 180.

In the power analysis for Aim 1, we indicated that a medium effect of the treatment on multisensory processing is expected (i.e., the a path for Aim 2). We have no pilot data for the b path because it is the association of multisensory processing with neurodevelopmental outcome *controlling for the treatment*. The proposed study is the needed RCT to estimate the effect size of the b path. However, a zero-order correlation between multisensory processing and motor and language Bayley standard scores was 0.41 to 0.42, respectively, in the previous correlational study on preterm infants. These are considered between medium and large effect

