### **Inclusion and Exclusion Criteria**

The study population was originally comprised of 200 preterm infants. Due to Covid 19 losses to follow up, this number has been revised to 230 preterm infants. We anticipate the distribution to be 45% male and 55% female, as females have a small survival advantage after extreme prematurity. All races and ethnicities will be included, with an expected skew towards slightly more black children due to disproportionate effects of prematurity on race.

Inclusion criteria includes PMA 32 0/7 weeks gestation-36 0/7 weeks gestation. Exclusion criteria will be ventilation using an endotracheal tube, major congenital malformations, family history of genetic hearing loss, and use of sedatives or seizure medications. These medications may mask sensory processing as assessed by ERPs.

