### **Randomization**

Random assignment to groups will be carried out using unified reproducible methods (i.e. saved random number seeds) provided by our Biostatistics core. We will try to conceal allocation from all study personnel who could influence scores. Except for parent reports, examiners will be blind to treatment assignment. We will obtain recorded parent's voice from both groups with the intent of masking parents to assignment. Although we cannot fully mask parents to group allocation, as bedside nurses communicate regularly with them, we will address the potential effect on the parent questionnaire at one-year by deemphasizing the sensory nature of the outcomes to both groups, and instead focusing on the proven positive links between parental involvement and improved intersubjectivity.

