## Protocol Title: Trial to Improve Multisensory Neural Processing, Language & Motor Outcomes in Preterm Infants

sizes. Finally, multisensory processing was associated with more typical behavioral thresholds to sensory stimuli in the home as evaluated on the Infant Toddler Sensory Profile in a previous correlational study with preterm infants. Thus, the expectation for an indirect effect that is at least the mid-point between small and medium is quite realistic.

Figure 3

*Our third aim is to explore the role of m responses in mediating intervention effects on later motor and language outcomes.*

*Plan:* An analogous analysis procedure as was proposed for Aim 2 will be used to test Aim 3. The putative mediators are the two unisensory processing (i.e., speech processing or touch) variables. The putative mediator is speech processing for the language outcome and the putative mediator is touch processing for the motor outcome.

*Statistical power:* The power analysis for Aim 2 applies to Aim 3. The expectation for an indirect effect that is at least the mid-point between small and medium is realistic. With regards to a path, the sample-size-adjusted standardized mean difference on speech processing effect size from the contingent parent-voice vs control (a treatment that is a subset of the proposed treatment) contrast was large (i.e., Hedges  $g = 1.06$ ). The proposed treatment will provide more nurturing touch than infants in control group and nurturing touch has been associated with better touch perception experience in our preliminary studies. The zero order correlation speech perception to later language was very large ( $R^2 = .39$ ) in the previous correlational study of preterm infants.

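### No analysis has a family term and no rule covers siblings: if siblings are enrolled, the mediation b path is mildly anti-conservative, and the Aim 1 tests are too if siblings are allocated together

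*Combined protocol and SAP*

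**What the plan says.** **Eligibility.** Under Inclusion and Exclusion Criteria, "Inclusion criteria includes PMA 32 0/7 weeks gestation-36 0/7 weeks gestation". The same section continues: "Exclusion criteria will be ventilation using an endotracheal tube, major congenital malformations, family history of genetic hearing loss, and use of sedatives or seizure medications". Twins, higher-order multiples and siblings are not mentioned.

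**Allocation.** Study Design and Setting and Study Procedures make the infant the unit randomised. The Randomization section adds: "Random assignment to groups will be carried out using unified reproducible methods". Neither place says whether siblings are randomised one by one, kept together or split.

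**Analysis.** Under Statistical Analysis, for continuous Aim 1 outcomes, "we will use ANOVAs when controlling for pretreatment variables", and otherwise "independent sample t-tests when there is no need for a covariate". For the categorical ITSP result: "When testing the nominal form of the sensory reactivity and adaptation outcome, we will use logistic regression". For Aim 2 the indirect effect "will be tested for significance using the bias-corrected bootstrap method", and for Aim 3: "An analogous analysis procedure as was proposed for Aim 2 will be used to test Aim 3". The unit that the bootstrap resamples is not stated. The candidate covariates listed under Randomization contain no family or multiple-birth term, and the power sections contain no design effect.

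**The concern.** Siblings in this trial would have much in common by design. They share the parents whose voice is recorded and who give skin-to-skin care, and normally the parent who completes the ITSP, BCQ and PSDQ. Their outcomes, and probably their ERP responses, can be expected to correlate.

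The named methods, used in their ordinary form, count each infant as an independent observation. Depending on how siblings are allocated, the standard error of the treatment contrast may then be too small, about right or too large. The mediation analysis has a separate exposure. The b path regresses one sibling-correlated variable on another, so randomising siblings separately does not protect it. At stake are the stated level of the Aim 1 tests and the credibility of the mechanistic claims in Aims 2 and 3.

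**Working it through.** **Inputs from the documents:** 230 infants, 115 per group; 180 used for power; one-tailed test for Aim 1 power; minimum effect g = 0.35. The significance level is not stated, so 5% is assumed.

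**Inputs assumed, because the documents give none:** share of infants in twin pairs f = 0.2-0.4; within-pair correlation of an Aim 1 outcome r = 0.3-0.7; for the b path, mediator correlation r_M = 0.5-0.7 and outcome correlation r_Y = 0.5-0.9.

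**1. The plan's own power figure, with independent infants.** At g = 0.35 and 90 per arm, power = Φ(0.35 × √45 − 1.645) = Φ(0.703) = 75.9% (75.6% by the exact t). The stated figure of over 80% is reached with 207 infants (80.6%), or with 180 if the baseline ERP correlates about 0.33 or more with the outcome. That gap is a separate matter. Here 75.9% serves only as the reference.

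**2. Aim 1 by allocation rule.** The design effect (DE) for the treatment contrast is:
- pairs allocated together: DE = 1 + f·r
- pairs always split: DE = 1 − f·r
- each infant randomised individually: a pair is concordant or discordant with probability ½ each, so the terms cancel on average and DE ≈ 1

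The true error of the unadjusted test is 1 − Φ(1.645/√DE) one-sided, or 2[1 − Φ(1.96/√DE)] two-sided.

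| Allocation | f, r | DE | One-sided | Two-sided |
|---|---|---|---|---|
| Together | 0.2, 0.3 | 1.06 | 5.5% | 5.7% |
| Together | 0.4, 0.7 | 1.28 | 7.3% | 8.3% |
| Split | 0.2, 0.3 | 0.94 | 4.5% | 4.3% |
| Split | 0.4, 0.7 | 0.72 | 2.6% | 2.1% |

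Simulation of the t-test at N = 180 agrees. For f = 0.2 and r = 0.5, one-sided error was 6.0% together, 4.9% individual and 4.0% split. Over all scenarios run (f = 0.2-0.4, r = 0.5-0.9), individual randomisation gave 4.8-5.2%.

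**3. Aim 1 power if pairs were kept together and the standard error were correct.** The effective N is 180/1.06 = 170 down to 180/1.28 = 141. Power at g = 0.35 falls from 75.9% to Φ(0.35 × √(169.8/4) − 1.645) = 73.7% and Φ(0.35 × √(140.6/4) − 1.645) = 66.7%.

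**4. The b path.** With treatment in the model, the variance of the b coefficient is inflated by about 1 + f·r_M·r_Y. Treatment assignment does not enter this expression.
- f = 0.2, r_M = 0.5, r_Y = 0.5: 1 + 0.05 = 1.05, two-sided error 5.6%
- f = 0.3, r_M = 0.5, r_Y = 0.7: 1 + 0.105 = 1.105, two-sided error 6.2% (simulated 6.3%)
- f = 0.4, r_M = 0.7, r_Y = 0.9: 1 + 0.252 = 1.252, two-sided error 8.0% (simulated 8.0%)

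These are levels for the regression test of b. A bootstrap that resamples infants carries the same understated variance; one that resamples families does not. The inflation passes to the indirect effect most fully when the a path is clearly non-zero, because the result then turns on b.

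**The case against.** The strongest reply is that the documents randomise infants and nowhere suggest that siblings are kept together. On that reading the Aim 1 tests hold their level even with many twins. This stands. A reader might infer from the silence on multiples that every standard error in the plan is wrong once siblings are enrolled. The documents do not support that: for Aim 1, an inflated error needs joint allocation, which the plan does not describe.

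Two other inferences go too far. The criteria do not admit every preterm infant in the age window, since four exclusions apply. Nor does the plan say that the bootstrap resamples individual infants; it leaves the unit open.

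It is also fair to say that the pretreatment ERP is always adjusted for under Power/Sample Size, so the ERP outcome goes through the covariate-adjusted model and not the plain t-test. The relevant correlation is then the residual one, which may be smaller. That model still has no family term.

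Finally, the twin share and correlations are assumptions. At f = 0.1 and r = 0.3 the joint-allocation design effect is only 1.03. None of this answers the b-path point, which does not depend on siblings being kept together.

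**Conclusion.** The point holds in a limited, conditional form. The plan permits siblings, gives no rule for allocating them and names no method that accounts for family. Whether any are enrolled cannot be told from the documents.

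If they are, Aim 1 is sound under individual randomisation, mildly anti-conservative under joint allocation and conservative if pairs are always split. The b path in Aims 2 and 3 is mildly anti-conservative under individual or joint allocation, at about 5-8% for a nominal 5%, unless families are resampled. All sizes rest on the assumed twin share and correlations. This is a minor improvement to the analysis and does not threaten the design.

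**What to change.** - State in the Randomization section that siblings are randomised individually, or say how else they are allocated.
- Record a family identifier for every infant.
- For Aim 1, use standard errors that account for family: GEE with robust errors, or a mixed model with a family effect, including for the categorical ITSP outcome.
- For Aims 2 and 3, state that the bootstrap resamples families.
- Carry the family identifier into the multiple imputation so that it matches the analysis.

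The cost is a few sentences in the plan, one data field and slightly more analysis work. Intervals for Aims 2 and 3 may widen slightly. If few multiples are enrolled, the effect on results is negligible. Settling this before analysis avoids a choice made after seeing the data.

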### **Analysis Plan**

#### **Power/Sample Size**

A total sample size of 230 (115 in each group) will be recruited. Although attrition in past similar work has been much lower, we estimate power under an assumption of 10% attrition (i.e., 180). Because pilot studies afford effect size estimates with wide confidence intervals due to small sample sizes, power analysis results were conducted for the effect size available from pilot data and lowest effect size that the after-attrition sample size affords. Feasibility of the expected effect size is then evaluated. Power analyses are based on primary variables (multi- and uni- sensory processing). If between-group differences occur on the putative covariates (i.e., pretreatment variables related to the outcomes) and they are associated with putative mediators or outcomes, the pretreatment variables will be statistically controlled after ensuring that the homogeneity of slopes assumption has been met. Pretreatment ERP variables will be statistically controlled regardless of the effect size of between-group differences to improve effect size estimates. Missing data will be handled using multiple imputation.

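### The power of over 80% at g = .35 does not follow from the printed inputs (75.6% with 180 infants, one-tailed, alpha .05 assumed), and 180 is not 230 less 10%

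*Combined protocol and SAP*

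**What the plan says.** Under Power/Sample Size the plan states "A total sample size of 230 (115 in each group) will be recruited". The next sentence says "we estimate power under an assumption of 10% attrition (i.e., 180". Under Inclusion and Exclusion Criteria we read "The study population was originally comprised of 200 preterm infants" and that, because of Covid-19 losses to follow-up, "this number has been revised to 230 preterm infants".

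The Aim 1 power paragraph under Statistical Analysis gives "the estimated power using a 1-tailed test" with 180 infants as over 99% at the pilot effect (Hedges g = .74). It adds that at g = .35 "we will have over 80% power to detect the effect under the proposed conditions".

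For the analysis of continuous outcomes, "we will use ANOVAs when controlling for pretreatment variables", with independent-sample t-tests where no covariate is needed. Power/Sample Size adds that "Pretreatment ERP variables will be statistically controlled regardless of the effect size of between-group differences". No alpha, no direction for the final test and no pre-post correlation appear anywhere in the document.

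**The concern.** Power/Sample Size acknowledges that pilot effect sizes carry wide confidence intervals. It therefore reports power both for the pilot effect and for the smallest effect that the post-attrition sample can support. The g = .35 sentence is that second figure, so it is the plan's margin if the pilot g of .74 proves optimistic. It bears on the primary outcome, the multisensory response.

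Two things looked wrong. The printed inputs appeared to give less than 80%. And the sample size used for power belongs to the earlier target of 200, not to the 230 named in the sentence before it. If the figure cannot be rebuilt, a reader cannot tell from the text whether the margin exists. An unstated test direction also leaves a choice that could be made after the data are seen.

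**Working it through.** **Inputs from the plan.** Two equal arms; 180 infants for power; 230 recruited; 10% attrition; original target 200; g = .35 and g = .74; one-tailed test for power.

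**Assumptions.** Alpha = .05, since none is stated. Unadjusted figures are for a two-sample t-test. Adjusted figures treat g as expressed on the unadjusted post-treatment SD.

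**Step 1: the figure that reproduces.** The noncentrality parameter is g × √(n₁n₂/(n₁+n₂)), with n₁+n₂−2 degrees of freedom. At g = .74 and 90 per arm it is .74 × √45 = 4.964 with 178 df. One-tailed power is 99.95%, which agrees with the plan's statement of over 99%.

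**Step 2: the figure that does not.** At g = .35 and 90 per arm it is .35 × √45 = 2.348 with 178 df. One-tailed power is 75.6% (75.9% by normal approximation). Reaching 80% here would need a one-tailed alpha of about .067, or g of about .372.

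**Step 3: the sample size.** 200 × 0.90 = 180, whereas 230 × 0.90 = 207. Going from 230 to 180 would be 1 − 180/230 = 21.7% attrition.

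**Step 4: unadjusted power at g = .35.**

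| Analysed n | One-tailed | Two-sided |
|---|---|---|
| 180 | 75.6% | 64.6% |
| 200 | 79.4% | 69.2% |
| 207 | 80.6% | 70.7% |
| 230 | 84.2% | 75.3% |

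Even the whole original 200, with no attrition, falls just short one-tailed. The one-tailed figure crosses 80% between 203 infants (79.96%) and 204 (80.13%). From 230 that allows at most 1 − 204/230 = 11.3% attrition. The smallest g with 80% power at 207 is .347 one-tailed and .391 two-sided; at 180 it is .372 and .420.

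**Step 5: credit for the pretreatment ERP.** With pre-post correlation r, the effect becomes g/√(1−r²) and one more degree of freedom is lost.

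| r | n = 180, one-tailed | n = 180, two-sided | n = 207, one-tailed | n = 207, two-sided |
|---|---|---|---|---|
| .3 | 79.0% | 68.7% | 83.8% | 74.8% |
| .5 | 85.4% | 76.9% | 89.5% | 82.5% |
| .6 | 90.0% | 83.1% | 93.2% | 87.9% |

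The r needed for 80% at n = 180 is about .34 one-tailed and about .55 two-sided. At n = 207 none is needed one-tailed, and about .45 is needed two-sided.

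**The case against.** The strongest reply is that the unadjusted t-test is not the planned analysis. The plan always controls the pretreatment ERP, and it bases power on the ERP variables, so the conditions of the claim may include that adjustment. A modest r of .34 then gives 80.0% at 180. This stands as a possible explanation. But the plan prints no r and the power sentence takes no explicit credit for a covariate, so the claim still cannot be checked. The adjusted figures also depend on the scale of g. Table 1 defines one primary variable as a pre-post change, and the document does not say which scale the .74 and .35 refer to. On a change-score scale, the r values in Step 5 would not apply.

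Second, correcting the sample size helps the sponsor: 207 gives 80.6% one-tailed without any adjustment. The ERP is recorded near discharge, and the plan reports under 5% data loss from electrode placement in earlier studies, so losses on this outcome may be smaller than 10%. That also stands, though the margin at 207 is only three infants above the 204 needed.

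Third, the only direction printed is one-tailed, and Aim 1 is worded directionally. The two-sided shortfall is therefore conditional. It is relevant because the analysis text gives no direction and the usual ANOVA F test is two-sided.

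Finally, 180 might be a deliberate evaluable target that allows for Covid losses. In that case the stated 10% is wrong instead, and the two figures still conflict.

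**Conclusion.** The concern holds. On the printed inputs, with alpha .05 assumed and no baseline adjustment, power at g = .35 is 75.6%, between 4 and 5 points below the claim. The 180 does not match 230 less 10%, which is 207.

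This is a power statement that does not follow from its inputs, not a demonstrated shortage of power. On the one-tailed premise the claim is met narrowly at 207. It also holds at 180 if r is about .34 or more, on the scale assumed above. If the final test is two-sided it falls short at 207 (70.7%) unless r is about .45 or more. The g = .74 statement is sound. Confidence is high on the non-reproduction and the outdated sample size. It should be fixed before the plan is relied on.

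**What to change.** 1. Under Power/Sample Size, reconcile 180 with 230 and 10% attrition, and carry the result into the power paragraph for Aim 2, which also uses 180 and is in turn applied to Aim 3.
2. State alpha and one test direction, once, for both the power statement and the analysis.
3. Say which scale g is on (post-treatment or change score).
4. Restate the Aim 1 power. Suggested wording: *With 207 analysable infants (230 less 10%), alpha .05 and no credit for baseline adjustment, power at g = .35 is 81% one-tailed or 71% two-sided (76% or 65% if only 180 are analysable).* Keep only the direction that is pre-specified.
5. If credit is taken for the pretreatment ERP, give the assumed pre-post correlation and its source and recompute. For example, r = .5 at 207 gives 82% two-sided, with g on the post-treatment scale.

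The cost is wording only, with no extra infants. The sponsor must commit to a test direction. The stated margin may also look slightly worse: if two-sided and unadjusted at 207, the smallest effect with 80% power becomes about g = .39 instead of .35.
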